In general, 3 to 24 hours prior to intervention a clopidogrel loading dose of 600 mg will be administered. In addition to clopidogrel the patient receives a loading with 250 mg ASA (orally or i.v.). The early dual platelet inhibition therapy is applied due the rapid offset of the anticoagulation effect upon termination of argatroban infusion at the end of the PCI. The offset of argatroban effect has been observed within 30 minutes after stop of the infusion. Thus, a potential gap of sufficient antithrombotic protection may be obtained if the dual antiplatelet therapy is only started after termination of argatroban infusion. The ARG-E04 study [5] revealed an effective and safe persistent antithrombotic protection if dual antiplatelet therapy was instituted before PCI commenced.

After getting an argatroban bolus dose of 300 µg/kg (administered over 3 to 5 min), the patient receives an argatroban maintenance dose infusion of 20 µg/kg/min. The argatroban infusion will be stopped at the end of the PCI (removal of the guiding catheter or the sheath).

To monitor reliability of anticoagulation, ACT will be measured as a routine parameter of anticoagulation for PCI. In general, ACT measurements will be started and performed with the placement of the vascular sheath (starting the intervention). Therefore, plasma samples will be obtained 5 minutes after completion of injection of the bolus dose and at 5 min after completion of every further bolus or treatment adjustment. Depending on clinical relevancy further ACT assessments are possible.

If target ACT is reached, the intervention can be continued.

If ACT remains below the target of 300 s, patients will receive an additional i.v. bolus injection of 150 µg/kg and the infusion dose will be raised up to 30 µg/kg/min. In case ACT > 450 s, the infusion dose will be reduced to 15 µg/kg/min. As soon as the target ACT (between 300 s and 450 s) is reached infusion dose shall remain unchanged during PCI procedure. If clinically necessary, the hematocrit value will be measured during the treatment.

The PCI will be conducted according to usual clinical routine of the investigator site. The PCI starts with the placement of the vascular sheath and ends with re-movement of this sheath. Immediately after PCI, a study-specific 12-lead ECG (ECG-2) will be recorded in the catheter lab at a time of steady state anticoagulation with argatroban.

Follow-up phase (ends > 8 but ≤ 28h after PCI):

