8.2. Dose and schedule of treatment

Efficacy and safety of argatroban have been investigated in the treatment of PCI patients without HIT II previously [5].

Patients will receive argatroban treatment in a dosing schedule adapted from the approved Argatra® Multidose SmPC with information status by July 2016, taking into account that due to the lack of HIT II in the study population a lower bolus and maintenance dose led to a rapid and sufficient anticoagulatory effect in the previous ARG-E04 study [5].

Since the anticoagulation effect of argatroban returns rapidly towards normal level, a possible gap in a sufficient continuous antithrombotic protection must be closed. To reduce the risk of early stent thrombosis, patients receive in accordance with the ARG-E04 study a dual platelet inhibition therapy with the **antiplatelet drugs** clopidogrel and ASA before start of the PCI. A clopidogrel loading dose of 600 mg is administered 3 to 24 hours prior to an elective angiography with high probability for PCI. In addition to clopidogrel, all patients receive a loading of 250 mg ASA (orally or i.v.). For patients on chronic DAPT with ASA and clopidogrel known being loaded there is no need for an additional loading prior to intervention.

After PCI, antithrombotic prophylaxis with DAPT will be conducted according to clinical routine and ESC guidelines.

With regard to treatment with the **anticoagulant** study medication argatroban, the patient will receive an i.v. bolus of 300 µg/kg argatroban administered over a span of 3 to 5 minutes before start of the intervention procedure, followed by the i.v. infusion of argatroban at 20 µg/kg/min until the end of the procedure. ACT will be checked 5 minutes after the initial bolus dose was administered. If ACT remains below the target of 300 s, the patient receives an additional i.v. bolus injection of 150 µg/kg and the infusion dose will be raised up to 30 µg/kg/min. In cases ACT > 450 s, the infusion will be reduced to 15 µg/kg/min and the value will be checked again after 5 minutes. As soon as the target ACT (between 300 s and 450 s) is reached, infusion dose shall remain unchanged during the PCI procedure. Depending on clinical relevancy further ACT assessments are possible.

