13.1. Sample size calculation

A one-sided one sample t-test with a significance level of 5% will be used to test the primary hypothesis of this study that QTc will not increase more than 10 ms under argatroban. Table 1 depicts the power of the test with 45 evaluable patients for varying population means Δ QTc.

Δ QTc in population	Power	β
0	> 0.999	< 0.001
1	> 0.999	< 0.001
2	> 0.999	< 0.001
3	0.999	0.001
4	0.990	0.010
5	0.951	0.049
6	0.841	0.159
7	0.632	0.368
8	0.373	0.627

Table 1: Power of test (one-sided one sample t-test, alpha=5%, n=45 evaluable patients)

Up to a population mean of Δ QTc = 6 the power of the test will be adequate, i.e. > 0.8 . To account for potential dropouts at least 50 patients will be enrolled into the study, assuming a dropout rate of about 10%.

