12.2 Secondary objectives

The secondary objectives are:

- Determination of the QTc interval after sufficient wash-out period by ECG-3 which needs to be performed > 8 but ≤ 28 hours after termination of prolonged argatroban infusion.
- Investigation of dependence of QTc interval on gender and applied doses.
- Determination of coagulation status during argatroban therapy.
- Assessment of safety-related events within the scope of anticoagulation with argatroban, for example bleeding events or thromboembolic events.

The secondary endpoints in this study are:

- Mean difference in QTc interval between ECG-3 and ECG-1.
- Proportion of patients with a prolongation of QTc interval to > 500 ms at ECG-2.
- Proportion of patients with a prolongation of QTc interval to > 500 ms at ECG-3.
- Proportion of patients with a prolongation of QTc interval of > 60 ms at ECG-2 compared to ECG-1.
- Proportion of patients with a prolongation of QTc interval of > 60 ms at ECG-3 compared to ECG-1.

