15.5 Efficacy evaluation

The primary data set for the efficacy analysis will be the ITT analysis set. Additional analyses will be performed for the PP analysis set. Note that whereas trials to show superiority always use the ITT population as primary analysis, results for both ITT and PP population are of interest in non-inferiority trials. It may actually be easier to show non-inferiority in the bigger sample of the ITT population, especially in case of many protocol deviations. This underpins the importance of the PP analysis in non-inferiority trials.

Subgroup analyses will be performed as described in Section 14.6.

Summary tables will be provided by means of descriptive statistics and frequency tables, as appropriate.

15.5.1 12-lead ECG

The following will be presented at screening, during treatment and at follow-up:

- Overall interpretation (investigator and blinded ECG-reader assessment); if abnormal, clinically significant
- Measured QT interval, corrected QT interval
- Interpretation of QT interval: prolonged; if prolonged, clinically significant

Primary endpoint (see section 12.1):

- Difference in QTc interval between ECG-2 and ECG-1 ($\Delta QTc = QTc_2 - QTc_1$)
- Test of statistical hypothesis (see Section 14.3)

Secondary endpoints (see section 12.2):

- Difference in QTc interval between ECG-3 and ECG-1 ($QTc_3 - QTc_1$)

- Proportion of patients with $QTc_2 > 500$ ms
- Proportion of patients with $QTc_3 > 500$ ms
- Proportion of patients with $QTc_2 - QTc_1 > 60$ ms
- Proportion of patients with $QTc_3 - QTc_1 > 60$ ms

In addition, a listing will tabulate the individual response data, i.e. QTc_1 , QTc_2 , QTc_3 as well as gender and cumulative Argatroban dose.

The dependence of QTc interval on gender and cumulative Argatroban dose will furthermore be investigated in plots. If applicable, linear correlation of QTc interval and cumulative Argatroban dose will be assessed.

Heart rate and Measured RR interval will be presented at screening, during treatment and at follow-up.

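### Argatroban dose is titrated to each patient's ACT, so the planned correlation of QTc with cumulative dose can understate a real exposure effect, most likely by coming out near zero

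*Protocol*

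**What the plan says.** Protocol 6.3 and 8.2 give every patient a 300 µg/kg bolus and then 20 µg/kg/min, with ACT checked 5 minutes after the bolus. From there the dose follows the ACT. Protocol 8.2: "If ACT remains below the target of 300 s, the patient receives an additional i.v. bolus injection of 150 µg/kg". Protocol 6.3 adds that "the infusion dose will be raised up to 30 µg/kg/min. In case ACT > 450 s, the infusion dose will be reduced to 15" µg/kg/min. Within 300 to 450 s the rate stays as it is. The infusion lasts as long as the PCI, up to 1 hour (Protocol 6.2).

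A secondary objective in Protocol 5.3 and SAP 12.2 is "Investigation of dependence of QTc interval on gender and applied doses". SAP 15.5.1 serves the dose part with a listing, plots against cumulative dose and one conditional statistic: "If applicable, linear correlation of QTc interval and cumulative Argatroban dose will be assessed". The outcome named is QTc, not its change from baseline. No ACT value, titration step or infusion duration enters. SAP 15.4 lists PCI duration, ACT values and dosing scheme per patient. Plasma concentration is measured only at follow-up, before ECG-3. SAP 14.4 makes any secondary p-values descriptive.

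**The concern.** Dose is meant to stand in for exposure, but here it was partly chosen in reaction to exposure. A patient who clears the drug quickly tends to have a low ACT and is given more; a slow clearer is given less. Titration therefore pulls concentrations together while it spreads doses apart. A drug that prolongs QTc with concentration could then show little relation between dose and QTc.

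Protocol 5.1 says that no QTc data on argatroban exist so far and that these data are needed for a planned marketing authorisation. A flat dose plot in that setting could be taken as reassurance. Neither document notes that dose depends on response, and with no concentration measured at ECG-2 nothing in the planned output would correct the impression.

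**Working it through.** **1. The plan's own figure.** The documents give no figure for the dose correlation. The only power figure is for the primary test, and it supplies the SD needed below. Inputs (Protocol 13.1): "A one-sided one sample t-test with a significance level of 5% will be used", margin 10 ms, 45 evaluable patients. The SD is not stated. With SD 10 ms the non-centrality is (10 - mean) × √45 / 10. At a mean of 6 ms this is 4 × 6.708 / 10 = 2.683, and with critical t (44 df) = 1.680 the power is 0.841, as in Table 1. Means of 4, 5, 7 and 8 ms give 0.990, 0.951, 0.632 and 0.373, also as printed. Back-solving gives an SD of 9.98 to 10.01 ms. Enrolment: 45 / 0.9 = 50. So a residual SD of 10 ms for ΔQTc is consistent with the plan.

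**2. What makes dose differ.** SAP 15.4 defines cumulative dose as boluses plus rate × duration. As a simplification, the adjusted rate runs from the start, the increase goes to the full 30, and there is one extra bolus (µg/kg):

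| Course | 30 min | 60 min |
|---|---|---|
| Reduced | 300 + 15×30 = 750 | 300 + 15×60 = 1200 |
| Unchanged | 300 + 20×30 = 900 | 300 + 20×60 = 1500 |
| Raised | 450 + 30×30 = 1350 | 450 + 30×60 = 2250 |

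At equal duration, every difference in dose per kg comes from the ACT. Duration matters too: the unchanged course gives 300 + 20×20 = 700 at 20 min against 1500 at 60 min.

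**3. Why this flattens the relation.** Near steady state, concentration is proportional to rate / clearance. Take relative clearances of 0.75, 1 and 1.5, with rates titrated to 15, 20 and 30. Then 15/0.75 = 20/1 = 30/1.5 = 20: the rate doubles and concentration does not move.

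**4. Simulation.** None of the kinetic inputs is in the documents. Assumed: one compartment, half-life 45 min, two ACT checks, titration at 300 and 450 s, median first ACT 380 s (340 s where marked *), residual SD 10 ms, true effect 10 ms at the median concentration (20 ms where marked †).

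| Between-patient variation | PCI, min | r, true effect with ΔQTc | r, cumulative dose with ΔQTc | Samples of 45 with r ≤ 0 |
|---|---|---|---|---|
| Kinetics CV 30% only | 40 | 0.14 | -0.01 | 54% |
| Kinetics CV 50% only | 40 | 0.24 | -0.06 | 66% |
| Kinetics CV 50% only † | 20–60 | 0.49 | +0.06 | 35% |
| Kinetics 30%, ACT sensitivity 30%, shared with QTc | 40 | 0.25 | -0.10 | 74% |
| Same | 20–60 | 0.28 | +0.01 | 49% |
| Kinetics 30%, ACT sensitivity 50%, shared * | 20–60 | 0.39 | -0.08 | 70% |
| Kinetics 30%, ACT sensitivity 30%, independent | 20–60 | 0.24 | +0.15 | 17% |
| Kinetics 10%, ACT sensitivity 30%, independent * | 20–60 | 0.25 | +0.23 | 6% |

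**5. Dose against concentration.** With PCI of 20 to 60 min, cumulative dose correlated positively with end-of-infusion concentration in all of 20 scenarios (+0.19 to +0.88), and in a wider grid of 40 (+0.12 to +0.89). With duration fixed at 40 min and only kinetics varying, it was -0.08 (CV 30%) and -0.27 (CV 50%).

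**6. Raw QTc as outcome.** With an assumed baseline SD of 20 ms, using QTc at ECG-2 instead of ΔQTc lowers the last two dose correlations in the table from 0.15 to 0.07 and from 0.23 to 0.11.

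**The case against.** The strongest objection is that the planned variable is cumulative dose, which contains PCI duration. The titration rule does not set duration, and a longer infusion before steady state raises both dose and concentration. That stands, and it is why dose and concentration stay positively related in step 5 once duration varies.

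A reader might infer that the planned analysis will give the wrong sign. The documents do not support that. No kinetic data are given, the simulated inverse correlations with ΔQTc reach only -0.10, and most arise with duration held fixed. The one inverse result with varying duration (-0.08) needs large ACT sensitivity that also governs QTc.

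A reader might also infer that the safety conclusion depends on this correlation. It does not. The correlation is conditional, secondary p-values are descriptive, dose dependence is an objective without a listed endpoint, and no decision rule uses it. That a flat plot would be cited as reassurance is a risk, not something that either document announces.

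Replacing dose by infusion rate and last ACT is not a safe remedy. Under Protocol 6.3 the infusion stops when the PCI ends, so none is running at ECG-2. ACT checks are required only after a bolus or adjustment, so the last value may be an early one. In simulation, rate plus last ACT often tracked concentration less well than cumulative dose alone (multiple R 0.61 against 0.77 in one scenario), and last ACT alone was sometimes negatively related to it.

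**Conclusion.** The point holds as a limit on interpretation and a modest gap in SAP 15.5.1. Because dose was titrated to response, the marginal correlation with cumulative dose can substantially understate a real exposure effect, and a value near zero is the likely false result. In the cases where kinetics varied alone or ACT sensitivity was shared with QTc, a true-effect correlation of 0.14 to 0.49 became -0.10 to +0.06, and 35% to 74% of samples of 45 gave zero or less. Where ACT sensitivity varies independently of QTc and is the main source of variation, little is lost (0.23 against 0.25).

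These sizes rest on assumed half-life, variability and effect; the planned output cannot show which case applies. The primary t-test and its power are unaffected.

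**What to change.** In SAP 15.5.1:

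1. Make ΔQTc (QTc₂ - QTc₁) the outcome for the dose objective instead of raw QTc.
2. Keep the cumulative-dose plot and add one exploratory model of ΔQTc on cumulative dose (or the last infusion rate before the stop), infusion duration and the last ACT recorded during PCI. Note that this ACT may be an early post-bolus value because later checks are optional. Cumulative dose and duration will be correlated, so read the model as a whole, not coefficient by coefficient. Adding terms to cumulative dose cannot lower the in-sample multiple R, so a higher R alone does not show that the confounding is removed.
3. State that a flat or negative marginal dose correlation will not be reported as evidence against an exposure effect, because dose was titrated to response.

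The inputs are already in the SAP 15.4 and 15.5.1 listings, so the cost is a few sentences and one model. The downside is wide intervals: three terms from about 45 patients. If only one change is made, the third gives most of the protection. No change to dosing is implied.

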6.4. Deviation from the study plan

The investigator must not deviate from the procedures described in the study protocol except if the safety of patients would be endangered.

Every protocol violation needs to be thoroughly documented and will be assessed as minor or major by the investigator and sponsor.

7. Trial population

7.1. Selection of trial population and assignment to treatment

The 50 patients to be included into the study will be recruited from patients who have been diagnosed with stable CAD or unstable angina (troponin negative) and who will be undergoing elective PCI at the study center.

Eligible patients who already signed the patient informed consent will be assigned a unique patient number (patient ID) at screening visit. The assigned patient ID of each patient has to be documented using a Patient Identification Log. The patient ID consists of two parts. The first part represents the center number, which is assigned to the investigator by the sponsor. The second part is the patient number which will be assigned sequentially within the center by the investigator. Once assigned to the patient, the patient number may not be reused.

7.2. Inclusion criteria

To be eligible for this trial, patients must meet following requirements:

- Diagnosis of stable CAD or unstable angina (troponin negative, i.e. within the normal range for the study site) with low to moderate anatomic risk.
- Patient requires elective percutaneous coronary angioplasty or stent insertion with an approved device in one or more de novo-treated or re-stenotic lesions in native vessels.
- Patient is on adequate platelet inhibition therapy after receiving a loading dose with ASA and clopidogrel before start of intervention
- Willingness to give written informed consent, written consent for data protection (legal requirement in Germany "datenschutzrechtliche Einwilligung") and willingness to participate and to comply with the requirements of the study protocol.
- The patient (female/male) is at least 18 years of age.
- Baseline ECG without changes that impair assessment of QTc interval.

7.3. Exclusion criteria

Patients with any of the following exclusion criteria will not be eligible for participation:

General exclusion criteria:

- Patient is indicated for highly complex 3-vessel intervention.
- The female patient is pregnant (exclusion by routine urine test) or is nursing during therapy period.
- Patients who are currently participating in another clinical trial or patients who participated in another clinical trial during the last 3 months prior to study start (date of treatment visit).
- History of drug, alcohol or chemical abuse within 6 months prior to study start.
- Planned surgical intervention other than study procedure within 7 days after study start.
- Any condition, which contraindicates the use of argatroban, or endangers the patient if he/she participated in this study.

Factors influencing QTc interval:

- Marked baseline prolongation of QTc interval (repeated demonstration of a QTc interval > 450 ms at baseline ECG).
- A history of risk factors of Torsade de pointes (e.g. heart failure, hypokalemia, family history of Long QT Syndrome).
- Known intraventricular conduction disturbance.
- Bradycardia: heart rate < 45 min⁻¹.
- Electrolyte level outside normal range (according to laboratory's reference values).
- The use of concomitant medications that interfere with the QTc interval.

- Intake of digitalis within the last 2 weeks before study start.
- Acute myocardial infarction or troponin-positive unstable angina.

Factors inhibiting use of argatroban in this study:

- Intolerance to ingredients of Argatra® (sorbitol).
- Known cirrhosis, hepatitis, clinically significant hepatic disorder at study start and/or history of clinically relevant hepatic disorder.
- Current hepatic disorder indicated by laboratory liver profile at screening: Bilirubin, AST/SGOT, ALT/SGPT, γ GT > 3.0 times upper limit of the normal (ULN).
- Renal insufficiency indicated by laboratory renal profile at study start: GFR < 35 ml/min.
- Uncontrolled hypertension (defined as blood pressure >180/120 mmHg).
- If any form of heparin was taken prior to study start and aPTT \geq 35 s.
- Intake of direct oral anticoagulants (DOAC) within 1 month prior to study start.
- If anticoagulants of type of vitamin K antagonists (VKA) were taken prior to study start and INR >1.2.
- Platelet count <125 \times 10⁹/l.
- Documented coagulation disorder or bleeding diathesis.
- Uncontrolled haemorrhage within the past 3 months.
- Uncontrolled peptic ulcer disease or gastrointestinal bleeding within the past 3 months.
- Cerebral aneurysm.
- Haemorrhagic stroke or ischaemic stroke in the past 6 months.

8. Treatment

8.1. Study medication

According to § 3 (3) GCP-V an investigational medicinal product is a pharmaceutical form of an active substance or placebo being tested or used as a reference in a clinical trial, including products already with marketing authorization but used or assembled (formulated or packaged) in a way different from the authorized form, or when used for an unauthorized indication, or when used to gain further information about the authorized form. In this study argatroban (trade name Argatra® Multidose) is the investigational medicinal product and neither placebo nor any comparator is used.

Investigational Medicinal Product

Argatra® is supplied in individually packaged vials as a concentrate for solution for infusion.

Active agent:

[REDACTED]

Pharmaceutical classification:

[REDACTED]

Chemical name:

[REDACTED]

Molecular weight: [REDACTED]

Molecular formula: [REDACTED]

Application: [REDACTED]

Qualitative and quantitative composition of the concentrate:

Ingredient	Concentration
[REDACTED]	[REDACTED]

8.2. Dose and schedule of treatment

Efficacy and safety of argatroban have been investigated in the treatment of PCI patients without HIT II previously [5].

Patients will receive argatroban treatment in a dosing schedule adapted from the approved Argatra® Multidose SmPC with information status by July 2016, taking into account that due to the lack of HIT II in the study population a lower bolus and maintenance dose led to a rapid and sufficient anticoagulatory effect in the previous ARG-E04 study [5].

Since the anticoagulation effect of argatroban returns rapidly towards normal level, a possible gap in a sufficient continuous antithrombotic protection must be closed. To reduce the risk of early stent thrombosis, patients receive in accordance with the ARG-E04 study a dual platelet inhibition therapy with the **antiplatelet drugs** clopidogrel and ASA before start of the PCI. A clopidogrel loading dose of 600 mg is administered 3 to 24 hours prior to an elective angiography with high probability for PCI. In addition to clopidogrel, all patients receive a loading of 250 mg ASA (orally or i.v.). For patients on chronic DAPT with ASA and clopidogrel known being loaded there is no need for an additional loading prior to intervention.

After PCI, antithrombotic prophylaxis with DAPT will be conducted according to clinical routine and ESC guidelines.

With regard to treatment with the **anticoagulant** study medication argatroban, the patient will receive an i.v. bolus of 300 µg/kg argatroban administered over a span of 3 to 5 minutes before start of the intervention procedure, followed by the i.v. infusion of argatroban at 20 µg/kg/min until the end of the procedure. ACT will be checked 5 minutes after the initial bolus dose was administered. If ACT remains below the target of 300 s, the patient receives an additional i.v. bolus injection of 150 µg/kg and the infusion dose will be raised up to 30 µg/kg/min. In cases ACT > 450 s, the infusion will be reduced to 15 µg/kg/min and the value will be checked again after 5 minutes. As soon as the target ACT (between 300 s and 450 s) is reached, infusion dose shall remain unchanged during the PCI procedure. Depending on clinical relevancy further ACT assessments are possible.

